8.3.2. Acceptability and impact on clinical and research staff

Semi-structured qualitative interviews with clinical and research staff will be undertaken to explore the effectiveness and efficiency of the trial processes. This will include:

- The effectiveness of the patient identification and screening processes.
- Identification of reasons for failure to recruit patients.
- The willingness of gynaecologists to take part.
- The effectiveness of the randomisation process.

Interviews will also ask for staff ideas for improvement in trial processes, and explore whether there are any unintended consequences of the trial procedure, which might have an impact on patient care processes or the organisation and management of care.

Up to 20 staff interviews will be undertaken, which will be spread evenly across the three sites and will include the main clinical and managerial roles affected by the trial. The interviews will be undertaken in the month following the discharge of the last trial patient home. The interviews are expected to last an average of 20-30 minutes, and will be recorded digitally.

8.4. Clinical outcomes

8.4.1. Primary Outcome

The primary outcome will be composite consisting of any of the following: intrauterine adhesions (see section 8.4.5 for details); severe bleeding (defined as that requiring blood transfusion or total blood loss \geq 500ml); infection and other post-operative complications (see section 8.4.5 for details); damage to the genital tract (cervical damage or uterine perforation); unsuccessful procedure (see section 8.4.6 for details).

8.4.2. Secondary Outcomes

- Rate of individual complications.
- Rate of serious adverse events.
- Need for additional surgical procedure(s) for miscarriage treatment.
- Need for medical management of miscarriage.

8.4.3. Procedure details

Components of the procedure considered as important include:

- The method of evacuation (manual vacuum aspiration, sharp curettage, suction curettage)
- When used, the size of the largest catheter used (measured in Hegar)
- The number of times a curette was passed into the uterine cavity
- Estimated blood loss (ml)
- Type of anaesthesia using for surgery
- Were uterotonic drugs used
- Was a balloon tamponade used
- Was antibiotic prophylaxis used
- Were products of conception observed

8.4.4. Intraoperative complications

Intraoperative complications are defined as any of the following:

- Anaphylaxis
- Bladder injury
- Uterine perforation
- Cervical damage
- Complications of anaesthesia
- Disseminated intravascular coagulation.
- Severe bleeding that requires a blood transfusion or total blood loss \geq 500ml.
- Death
- 'Other' we will collect complications that are not covered by the above list, which
 maybe included in the substantive study if they are thought to be relevant.

8.4.5. Post-operative complications

With the exception of intrauterine adhesions, these will need to have occurred within two weeks of treatment and are assessed 2-4 weeks following the procedure. Post-operative complications are defined as any of the following:

- Infection, with a definition based on CDC criteria and other studies as **two** or more of the following (without any **other** obvious cause of infection on history and examination): (1) uterine tenderness, (2) offensive vaginal discharge, (3) high temperature (4) white blood cell count > 12×10^9 /L. To assess this, the patient will be contacted and asked whether they have suffered from: (1) pelvic pain beyond two days of the surgery, (2) offensive vaginal discharge, (3) fever or chills. If they report two or more of these patient-related symptoms then they will be invited in for clinical assessment in line with good clinical practice
- Haemorrhage requiring blood transfusion
- Disseminated intravascular coagulation
- Unplanned hospital admission due to a post-operative complication
- Intrauterine adhesions (defined as the formation of any filmy adhesions) identified at 4-8 weeks following the procedure with hysteroscopy. Pictures of the uterine cavity will be taken and passed on to hysteroscopists blinded to the randomisation. There will be up to five hysteroscopists who will make a majority decision on the presence of the intrauterine adhesions.
- Death

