3.4. Assessment of Risk

The safety of the ultrasound is well established. The current consensus is there are no negative side effects to the patient if performing diagnostic ultrasound according to current regulatory guidelines (15).

The risks of the surgical management of miscarriage are outlined within the Royal College of Obstetrics and Gynaecology consent for surgical evacuation of the uterus for early pregnancy loss (16). The serious risks include: uterine perforation (5 in 1000 women) which may require laparoscopy or laparotomy to diagnose or treat organ injury; significant trauma to the cervix (1 in 1,000 to 10,000). Frequent risks include: bleeding that lasts for up to two

weeks is very common but bleeding leading to blood transfusion is uncommon (1-2 in 1,000 women); pelvic infection (3 in 100 women); repeat surgical management (5 in 100 women).

The alternatives include medical management with mifepristone and prostaglandins or expectant management, particularly without an intact gestational sac. These alternatives are associated with heavier and longer bleeding and a 15-50% chance of requiring surgical treatment either as an emergency or the woman's preference.

This trial is categorised as:

Type A: No higher than the risk of standard medical care

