8. OUTCOME MEASURES AND STUDY PROCEDURES

8.1. Clinical assessments and procedures

Procedural and baseline information will be collected prospectively during the intervention. Researchers will input the data directly onto a specifically created case report form. Baseline demographic information will include the patient's age, BMI, gestation, parity, if general anaesthesia is to be used, and type of miscarriage. The type of miscarriage included in this trial will be those diagnosed with early embryonic demise which is a delayed or missed miscarriage: The NICE guidance will be followed for the diagnosis of miscarriage (See box 1).

Following randomisation, the surgical procedure for the management of miscarriage will be conducted with or without intraoperative ultrasonography

Two to four weeks later, patients will be contacted to assess whether they have developed an infection after the procedure.

Four to eight weeks after the procedure, patients will undergo a follow-up hysteroscopy in the office setting without general anaesthesia. This is solely to identify if any intrauterine adhesions have formed following the surgical management of miscarriage. This is an important outcome because the prevalence of intrauterine adhesions is underestimated by clinicians and is thought to be related to the number of curette insertions and how vigorously the curettage in performed [18,19]. Two cohort studies reported 8-19% of women had intrauterine adhesions after surgical management of miscarriage [18,19]. Moreover, intrauterine adhesions can lead to menstrual disorders, infertility, pelvic pain and endometriosis.

Box 1. NICE guidance for diagnosis of non-viable intrauterine pregnancy

1.4.5

When performing an ultrasound scan to determine the viability of an intrauterine pregnancy, first look to identify a fetal heartbeat. If there is no visible heartbeat but there is a visible fetal pole, measure the crown–rump length. Only measure the mean gestational sac diameter if the fetal pole is not visible. 1.4.6

If the crown-rump length is less than 7.0 mm with a transvaginal ultrasound scan and there is no visible heartbeat, perform a second scan a minimum of 7 days after the first before making a diagnosis. Further scans may be needed before a diagnosis can be made.

1.4.7

If the crown-rump length is 7.0 mm or more with a transvaginal ultrasound scan and there is no visible heartbeat:

- seek a second opinion on the viability of the pregnancy and/or

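### The telephone rule for infection in Section 8.4.5 asks for two of three symptoms, so it does not reach women who meet the two-of-four definition with one symptom plus a raised white cell count

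*Protocol*

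**What the plan says.** Protocol Section 8.4.5 gives the case definition: "Infection, with a definition based on CDC criteria and other studies as two or more of the following". The four criteria are "1) uterine tenderness, (2) offensive vaginal discharge, (3) high temperature (4) white blood cell count", the last with a threshold of 12 × 10^9/L, and no other obvious cause may be present.

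The same bullet then says how the definition is to be assessed. The woman is contacted and asked about three things: "1) pelvic pain beyond two days of the surgery, (2) offensive vaginal discharge, (3) fever or chills". Next comes the rule for going further: "If they report two or more of these patient-related symptoms then they will be invited in for clinical assessment". Nothing is said about a woman who reports only one symptom.

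Section 8.1 gives this contact the same purpose: "Two to four weeks later, patients will be contacted to assess whether they have developed an infection after the procedure". Section 8.4.1 makes infection a component of the composite primary clinical outcome. The schedule in Section 8.5 lists no blood test at any visit.

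**The concern.** The definition and the rule meant to apply it have different thresholds. A white cell count cannot be reported over the telephone, and uterine tenderness is found on examination. A woman with fever alone and a raised count meets the definition. She would report one symptom, however, and the rule does not call for the assessment at which the count would be taken. The same holds for discharge alone or pain alone with a raised count.

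Two uses of the pilot are affected. Section 2.1 asks whether the outcome tools are adequate, and a tool that cannot fully apply its own definition bears directly on that question. Sections 2.1 and 13.1 also say that the pilot's clinical data will partly inform the sample size of the substantive trial. An incompletely ascertained component would carry through to the composite rate.

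**Working it through.** The protocol gives no figure for this point, so the check compares the two rules and then considers scale.

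**Inputs.** Definition: at least 2 of 4 criteria (8.4.5). Rule for invitation: at least 2 of 3 symptoms (8.4.5). Infection risk: 3 in 100 (3.4). Sample size: 90 (13.1).

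**Matching (an assumption).** Pelvic pain is paired with uterine tenderness, discharge with discharge, and fever or chills with high temperature. The white cell count has no counterpart among the symptoms.

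**Counting patterns.** Four yes/no criteria give 2^4 = 16 patterns.

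- Meeting the definition: C(4,2) + C(4,3) + C(4,4) = 6 + 4 + 1 = 11.
- Triggering an invitation: at least two of the three non-laboratory items, with the count either way: [C(3,2) + C(3,3)] × 2 = 4 × 2 = 8.
- All 8 have at least two criteria, so all lie inside the 11.
- Meeting the definition without an invitation: 11 − 8 = 3.

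| Pattern | Criteria met | Symptoms reported | Definition | Invited by the rule |
|---|---|---|---|---|
| Tenderness + raised count | 2 | 1 | met | no |
| Discharge + raised count | 2 | 1 | met | no |
| Temperature + raised count | 2 | 1 | met | no |

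In each of the 8 invited patterns the definition is already met without the count. Under this matching the fourth criterion therefore adds no case by this route.

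**Scale.** 90 × 0.03 = 2.7 expected infections. If a share s of definition-positive women have exactly one symptom plus a raised count, and nothing else finds them, the recorded rate is 3.0% × (1 − s). The protocol gives no s. Assumed values show the range:

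- s = 10%: 3.0% × 0.90 = 2.7%, a loss of 0.27 women in 90.
- s = 40%: 3.0% × 0.60 = 1.8%, a loss of 1.08 women in 90.

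A simple model does not narrow s. Suppose the criteria are independent, each symptom has probability p and a raised count has probability w. Then s = 3p(1−p)²w / [3p(1−p)²w + 3p²(1−p) + p³].

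- p = 0.30, w = 0.10: 0.0441 / (0.0441 + 0.2160) = 17%.
- p = 0.05, w = 0.50: 0.0677 / (0.0677 + 0.0073) = 90%.

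Real criteria are correlated, so neither value is an estimate. They show only that the share depends entirely on what is assumed.

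**The case against.** The strongest reply is that a case definition and a telephone trigger do different jobs, and that a screen which trades some sensitivity for less burden is a legitimate choice. That is fair in general. Here, though, the protocol presents the contact as the means of assessing the definition and states no such trade-off.

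Several stronger readings are tempting, and the documents do not support them.

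- *This contact is the only scheduled check for infection.* It is not. Adverse events are recorded at every visit in Section 8.5, pelvic infection is a listed event in 9.2, and reporting runs to 6 weeks after surgery (9.4). Unplanned admission for a post-operative complication is a separate item in 8.4.5. None of these applies the two-of-four test, so the mismatch remains.
- *A woman with one symptom drops out of follow-up, or is never assessed.* All participants are due a hysteroscopy at 4-8 weeks (8.1). Section 8.4.5 does not forbid inviting other women, and 7.3 leaves other management to local investigators. A count taken in usual care could still satisfy the definition. What holds is narrower: the stated rule does not call for the assessment.
- *The rule can only miss cases, so the recorded rate must be too low.* Pelvic pain is broader than uterine tenderness, and fever or chills is broader than high temperature. Section 8.4.5 does not say how a woman with two symptoms who is not examined is classified. The net direction is therefore not fixed. The broader wording also means that, without one-to-one matching, the count could decide a case in a woman who reports two symptoms but has one confirmed sign. It does not bring in a woman who reports only one symptom.

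Timing also limits what a wider trigger would gain. Complications must arise within two weeks, but the contact is at 2-4 weeks, so a count first taken afterwards is weak evidence about that window.

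Finally, the numbers are small. The exact 95% interval for 3 events in 90 is 0.7% to 9.4%, far wider than a move from 3.0% to 1.8%. The rule is the same in both arms, the pilot does not aim to determine effectiveness, and 2.1 singles out intrauterine adhesions for the sample size. These points limit the weight of the concern but do not remove it.

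**Conclusion.** The mismatch is real: 3 of the 11 criterion patterns that meet the infection definition do not trigger the assessment meant to apply it. The count of 3 rests on matching symptoms to signs one-to-one. It counts patterns, not women.

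The consequence is possible under-ascertainment of one component of the composite, of a size the documents do not allow to be estimated. With about 2.7 infections expected in 90 women, the absolute loss in the pilot is small. The 3 in 100 is itself a general consent-advice risk, not a rate under this definition. No power or sample size figure in the protocol changes. The point is worth acting on because the pilot is meant to test its outcome tools, and as written it would not show how many women fall between the two rules.

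**What to change.** Reconcile the telephone rule with the definition in Section 8.4.5. Whom to invite for assessment is for the clinical team to decide; this review does not say which of the two rules is right.

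For outcome classification, separately from clinical care:

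- For every woman reporting at least one of the three symptoms, use any temperature, examination finding, white cell count or infection diagnosis already in the hospital or GP record, together with the adverse event data.
- Report the number of women with exactly one symptom separately by arm, so that the pilot can judge whether the tool is adequate for the substantive trial.

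The cost is a small change to the wording and the follow-up form, plus a limited number of record checks. Records cannot supply counts that were never taken, so some women with one symptom will remain unclassifiable. Reporting that group separately makes the gap visible.

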8.4.6. Unsuccessful procedure

Failed treatment is defined as any of the following:

IRAS ID: 253447

- Failure to completely remove the products of conception during the initial evacuation.
- Positive pregnancy test three weeks after the procedure.
- Repeat surgical evacuation procedure(s) are required before telephone follow-up 2-4 weeks following the procedure.

• Medical management of miscarriage is required before telephone follow-up 2-4 weeks following the procedure.

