6.3. Randomisation

Randomisation will be provided by a secure online randomisation system at the Birmingham Clinical Trials Unit (BCTU) (available at www.bctu-redcap.bham.ac.uk/SEEU). Unique log-in usernames and passwords will be provided to those who wish to use the online system and who have been delegated the role of randomising participants into the study as detailed on the SEE U Trial Signature and Delegation Log. The online randomisation system will be available 24 hours a day, 7 days a week, apart from short periods of scheduled maintenance. A telephone toll-free randomisation service ([name]) is available Monday to Friday, 09:00 to 17:00 UK time, except for bank holidays and University of Birmingham closed days.

After participant eligibility has been confirmed by a research nurse or doctor and informed consent has been received, the participant can be randomised into the trial. Paper based randomisation notepads will be provided to investigators and may be used to collate the necessary information prior to randomisation. All questions and data items on the

Randomisation Notepad must be answered before a Trial Number can be given. If data items are missing, randomisation will be halted, and the randomisation process restarted in the trial database once the information is available. Only when all eligibility criteria have been provided will a Trial Number be allocated.

Participants will be randomised at the level of the individual in a 1:1 ratio to either surgical evacuation of products of conception with intraoperative ultrasonography or surgical evacuation of products of conception without intraoperative ultrasonography.

Random permuted blocks of variable length will be used to ensure that the staff recruiting participants to the trial cannot reliably predict the next allocation. To ensure balance in the treatment allocation, randomisation will be stratified by the following variables:

- Proposed anaesthesia type (none/local or general);
- Randomising site

Full details of the randomisation specification will be stored in a confidential document at BCTU.

Following randomisation, a confirmatory e-mail will be sent to the randomising clinician, local PI, local Research Nurse and trial co-ordinating office.

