6.5. Blinding

This will be an open trial design. It will not be possible to blind the surgeon from the use of ultrasound during the surgical management of miscarriage. If the procedure is performed under a general anaesthetic then the patient will be blinded from the intervention, but it will be obvious to the patient that ultrasound is being used if the surgical management of miscarriage is performed using local anaesthetic. Due to staffing restrictions it will not be possible to guarantee that the surgeon performing the hysteroscopy was not involved in the surgical management of miscarriage.

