7.2. Intraoperative ultrasound

With intraoperative pelvic ultrasound the clinician is free to follow their usual procedure for evacuation of the contents of the uterine cavity. However, a second person performs a simultaneous abdominal pelvic ultrasound to allow visualisation of the cervix and uterine cavity.

Those performing the ultrasound and the surgeon need to be competent to use the ultrasound safely, as determined by their local hospital competency assessments. Training will be provided by the Chief Investigator on the correct use of ultrasound guidance for both surgeons and assistants in order to ensure the correct technique is used. Clear views of the uterine cavity and cervix are vital to ensure the safety of the procedure. When clear views are not possible due to increased bowel gas or patient adiposity it may be necessary to fill the urinary bladder with warm saline to ensure an acoustic window to improve visualisation of the uterus.

These scans are painless and safe. Unlike X-rays and other imaging tests, they do not use radiation. They have not been found to cause any problems or complications. Once the cavity appears empty on ultrasound the procedure is stopped.

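### Incomplete removal at the first evacuation triggers the primary composite on its own, but has no method of assessment common to both arms

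*Protocol*

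**What the plan says.** Section 8.4.6 of the protocol opens with "Failed treatment is defined as any of the following" and gives four items. The first is "Failure to completely remove the products of conception during the initial evacuation". The other three are a positive pregnancy test at three weeks, a repeat surgical evacuation, and medical management, the last two before the telephone follow-up. Section 8.4.1 makes unsuccessful procedure, as defined in 8.4.6, one component of the primary composite.

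In the ultrasound arm, section 7.2 states that "a second person performs a simultaneous abdominal pelvic ultrasound to allow visualisation of the cervix and uterine cavity", and then: "Once the cavity appears empty on ultrasound the procedure is stopped". The comparator in section 6.3 is "surgical evacuation of products of conception without intraoperative ultrasonography", and no corresponding end point for the operation is described for it.

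On blinding, section 6.5 says: "It will not be possible to blind the surgeon from the use of ultrasound during the surgical management of miscarriage". Blinded reading is specified in one place only, for the hysteroscopy pictures used to decide on adhesions (8.4.5).

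**The concern.** The first item in 8.4.6 is enough by itself to make a participant a primary-outcome event. It refers to the state of the uterine cavity at the end of the first operation. One arm has a real-time view of that cavity and an image-based point at which the operation ends. The other arm has neither, by design. The protocol does not say who decides that removal was incomplete, by what means, when, or against what criterion.

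The chance that a truly incomplete evacuation is written down as such may therefore depend on allocation. The scan may reveal residue that would pass unnoticed in a control participant, which would push the composite against ultrasound. Alternatively, an operation that ended on an image of an empty cavity may seldom be recorded as incomplete, which would push the composite in favour of ultrasound. In either case the composite can differ between arms without any difference in what happened to the women. Section 13.1 says the substantive trial will be powered on this composite, and section 2.1 says the pilot's clinical data will inform its sample size.

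**Working it through.** The protocol states no figure for this item, so there is nothing to reproduce. The check is first textual and then a small illustration.

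**Is there a completeness check common to both arms?**

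- *Procedure details (8.4.3).* Both arms record "Were products of conception observed". Seeing tissue does not show that the cavity is empty.
- *Post-procedure scan.* None is required. Section 7.3 leaves all management other than the allocated scan to local discretion, so a control-arm scan is neither required nor excluded.
- *Hysteroscopy at 4-8 weeks (8.1).* Both arms have it, but its stated sole purpose is to look for adhesions.
- *Blinded panel (8.4.5).* It reads for adhesions only.

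None of these supplies a common check. The other three items in 8.4.6 are worded identically for both arms, so the first item is the exception.

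**Illustration of size, with no true effect**

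Inputs:
- *t*, the true rate of incomplete removal, equal in both arms. Assumed 5-15%. The low end borrows the only related rate in the protocol, 5 in 100 for repeat surgical management (3.4).
- *s*, the chance that a true case is recorded, by arm. Assumed; the protocol gives nothing.
- *o*, the rate of all other components combined. Assumed 15-25%. Protocol figures for adhesions (8-19%, section 8.1), infection (3%) and repeat surgery (5%, both section 3.4) give a similar span if treated as independent: 1 - 0.92 × 0.97 × 0.95 = 15.2% and 1 - 0.81 × 0.97 × 0.95 = 25.4%.
- About 45 women per arm (90 at 1:1, sections 13.1 and 6.3).

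Formula, assuming independence: recorded composite = 1 - (1 - *o*)(1 - *t* × *s*).

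Worked case, *t* = 5%, *o* = 15%:
- recording 90%: 1 - 0.85 × (1 - 0.045) = 18.8%
- recording 50%: 1 - 0.85 × (1 - 0.025) = 17.1%
- relative risk (RR), ultrasound to control: 17.1/18.8 = 0.91 if ultrasound has the lower recording, and 18.8/17.1 = 1.10 if it has the higher.

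All cases, ultrasound v control:

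| *t* | Recording *s* | *o* = 15% | *o* = 25% |
|---|---|---|---|
| 5% | 50% v 90% | 17.1% v 18.8%, RR 0.91 | 26.9% v 28.4%, RR 0.95 |
| 5% | 90% v 50% | 18.8% v 17.1%, RR 1.10 | 28.4% v 26.9%, RR 1.06 |
| 15% | 50% v 90% | 21.4% v 26.5%, RR 0.81 | 30.6% v 35.1%, RR 0.87 |
| 15% | 90% v 50% | 26.5% v 21.4%, RR 1.24 | 35.1% v 30.6%, RR 1.15 |
| 15% | 90% v 30% | 26.5% v 18.8%, RR 1.41 | 35.1% v 28.4%, RR 1.24 |

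At *t* = 5% with recording of 90% and 50%, the expected recorded cases are 45 × 0.045 = 2.0 and 45 × 0.025 = 1.1, a difference of about one woman. If *s* is equal in both arms, or the item is dropped, the RR is 1.00 throughout.

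Independence probably overstates the distortion. A woman with retained tissue who goes on to repeat evacuation, medical management or a positive test already counts through another item.

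**The case against.** Several points on the other side have force.

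- *It is a pilot.* Section 2.1 says the aim is not to determine relative effectiveness, section 13.2 calls the study too small for reliable analysis of effect, and the adequacy of outcome tools is itself under test. This stands, and it lowers the severity. It does not remove the point, because the composite and its rate are what the pilot passes on, and section 13.2 still allows relative risks with confidence intervals.
- *A case report form or analysis plan may define the item.* It may. But the protocol fixes the primary outcome in 8.4, and an analysis plan cannot supply control-arm observations that were never made.
- *More complete removal is the hypothesised benefit (1.1, 1.2.3).* A lower count with ultrasound could indeed be a true effect. That is a reason to measure it comparably, since as defined a true effect and a recording difference cannot be told apart.

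A reader might also infer more than the text supports. The protocol does not say that the unblinded surgeon judges completeness, nor that the scan certifies it. In 8.4.6 the reference to the initial evacuation says when removal failed, not when or by whom that is established. Section 7.2 says when the operation ends, and a cavity that appears empty does not bar a later finding of retained tissue. The control arm also has some information, since observed products are recorded. Differential recording is therefore an inference from a missing common method plus a one-arm image.

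A reader might also build a baseline composite from the complication rates in 3.4 and 8.1 and subtract several points for this item. Those rates do not include the item, so that subtraction does not follow.

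**Conclusion.** The concern holds as a gap in definition. An item sufficient alone for the primary composite has no assessor, method or criterion common to both arms, while one arm has an image of the very thing being judged. Its recorded frequency can differ by arm without a true effect, and the protocol does not allow the direction to be settled.

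At the only related rate in the document (5%), the assumed recording gap moves the composite relative risk to about 0.91-0.95 or 1.06-1.10. The distortion grows at higher true rates. These values rest on assumed recording probabilities, an assumed rate for the other components, and independence; they show scale and are not estimates. Large spurious effects would need true rates well above 5% or a wider recording gap, and the documents give no ground for either.

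Because the pilot draws no efficacy conclusion, the harm is to the composite rate and effect estimate carried into the substantive trial. It should be fixed before that happens, but it does not invalidate the pilot.

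**What to change.** Take the first item of 8.4.6 out of the composite and report it descriptively, by arm, with the procedure details in 8.4.3. Define unsuccessful procedure by the three items worded alike for both arms: the three-week pregnancy test, repeat evacuation and medical management. The pregnancy test has no row of its own in the schedule in 8.5, so the schedule should show it if the definition relies on it.

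Alternatively, keep the item only if completeness is established by one stated method, assessor and time point, applied identically in both arms and using data already collected. Reading retained tissue from the hysteroscopy pictures would not fit as the protocol stands, because 8.1 limits that examination to adhesions.

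The cost is a change of outcome wording and a relabelled form field. There would be slightly fewer composite events, and an acknowledged incomplete evacuation with no later consequence would no longer count. The remaining items are not free of bias either: repeat surgery and medical management are local decisions (7.3) in an open trial (6.5), so they are defined alike but could still be influenced by knowledge of allocation.
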